**Personalized Feedback Integrated Intervention.** The PFI will be modeled from those that have focused on substance use and targeted negative mood symptoms. The PFI will provide brief personalized feedback that delivers salient points on patterns of use, norms comparisons, AS, and coping strategies, and detailed text about the relation between perceived norms and behavior as well as the link between smoking and AS. First, the PFI will provide smoking feedback. Specifically, descriptive feedback on the participant's smoking behavior, history, and current nicotine dependence, perceived norms and actual norms of smoking in Texas and the US, personalized feedback on methods used to help them quit in the past and problems experienced while trying to quit in the past, feedback on money spent on smoking, health problems resulting from smoking and health benefits of quitting, perceived barriers to cessation, their smoking triggers as well as tips for quitting, managing cravings, and coping without smoking. Second, the PFI will define AS and provide information linking smoking and negative mood and the prevalence of their cooccurrence. For this portion of the PFI, participants will receive personalized feedback on smoking to cope with their negative mood, AS symptoms they endorsed, their overall AS score and a normative comparison for overall AS score among smokers, personalized feedback on rating of importance and confidence to change their AS, and coping strategies they indicated they used or were willing to use as well as additional coping strategies to help manage their AS and negative mood.

**Smoking Information Control.** Participants in the smoking information control group will receive the same computer-delivered smoking information content as the PFI condition, including smoking cessation strategies from the CTA pamphlet, but no personalized feedback or AS information. We have successfully used a similar control condition in intervention trials. The two conditions will be time matched. The use of this control will permit evaluation of personalized feedback for smoking/mood compared to non-personalized smoking content.

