The primary analysis strategy will consist of examining mean differences between the intervention and control group using general linear mixed modeling and evaluating expectancies and norms as mediators of intervention effects. With respect to evaluating the main effects of experimental conditions on dependent measures, each participant will provide baseline and 1-month follow-up data. I will employ an intent-to-treat design and correct for alpha inflation using Bonferroni adjusted alpha. I will examine mean differences for the different dependent variables (outcomes) at 1-month follow-up controlling for the baseline score on the outcome. As covariates, we will also include any demographic variable(s) on which baseline differences are evident in any of the outcomes variables. We will assess whether interventions are significantly different for outcomes at the follow-up point. I will be sensitive to distributional assumptions and will incorporate negative binomial or alternative distributional specifications as appropriate. My first aim focuses on intervention effects on smoking motivation (motivation, confidence, intention to quit and perceived barriers for quitting) as primary dependent variables. My second arm focuses on intervention effects on behavior outcomes (smoking rate, quit attempts, reinforcing nature of smoking, and coping-oriented smoking) as primary dependent variables. My third aim focuses on intervention effects on AS, anxiety/depressive symptoms, and willingness to use coping strategies as primary dependent variables. These criterion variables were selected on the basis of their theoretical and clinical relevance to the study questions and utility. Intervention condition will be included as a dummy coded contrast. Lastly, I will follow the procedures described by MacKinnon and colleagues to assess hypothesized mediation effects of decreased positive expectancies and perceived smoking norms for continued smoking; whereby, path A is the effect of the predictor on the mediator, path B is the effect of the mediator on the outcome, path C is the effect of the predictor on the outcome, and path C' is the effect of the predictor on the outcome controlling of the mediator. All mediation analyses will be temporally ordered such that mediators will be assessed immediately post-intervention and outcomes will be assessed at a later time point than the mediators; baseline scores for mediators and outcomes will be controlled for in mediation analyses. Mediation analyses will be conducted using bootstrapping techniques through PROCESS, a conditional modeling program that utilizes an ordinary least squares-based path analytical framework to test for both direct and indirect effects. An indirect effect is assumed to be significant if the product of paths A and B is significant.

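### Does the unstated significance level for the mediation tests leave part of the primary analysis without a valid rule?

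*Combined protocol and SAP*

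**What the plan says.** The Statistical Analysis Plan opens its quantitative part with two components: "The primary analysis strategy will consist of examining mean differences between the intervention and control group", by mixed modelling, and "evaluating expectancies and norms as mediators of intervention effects".

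On multiplicity it says: "I will employ an intent-to-treat design and correct for alpha inflation using Bonferroni adjusted alpha". The sentence just before that reads: "With respect to evaluating the main effects of experimental conditions on dependent measures, each participant will provide baseline and 1-month follow-up data". No overall alpha, divisor or family of tests is given.

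The three aims then name the primary outcomes: four on motivation, four on behavior, and three on anxiety sensitivity, mood and coping (four if anxiety and depressive symptoms are scored separately).

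Mediation comes last. The purpose is to "assess hypothesized mediation effects of decreased positive expectancies and perceived smoking norms for continued smoking". The plan defines paths A, B, C and C', and states that "mediators will be assessed immediately post-intervention" with outcomes measured later. It adjusts for baseline values of both and uses bootstrapping in PROCESS. The decision rule is "An indirect effect is assumed to be significant if the product of paths A and B is significant". Confidence level, interval type and number of resamples are not stated.

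**The concern.** Mediation sits inside the primary strategy, so it cannot be set aside as exploratory on the plan's own wording. The Bonferroni sentence stands in text about main effects and does not mention indirect effects. A reader could therefore conclude that mediation is tested uncorrected, or corrected by an unknown divisor.

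The consequences run both ways. The product test is conservative when both paths are null, but it runs at about its nominal size when the intervention moves the mediator and the mediator does not affect the outcome. That case is plausible for norms: the section on the personalized feedback intervention describes feedback on "perceived norms and actual norms of smoking in Texas and the US", and the mediators are measured straight afterwards. Many pairs tested at 0.05 could then yield false claims of mediation. A large divisor would instead cost much of the power for a true mediator. If neither the pairs nor the divisor is fixed, either could be chosen after the data are seen.

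**Working it through.** The plan states no alpha, power or sample-size derivation, so there is no figure of its own to reproduce.

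**1. Number of pairs.** Outcomes: 4 + 4 + 3 = 11, or 4 + 4 + 4 = 12. Two mediators give 22 or 24 pairs.

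**2. Possible levels, assuming overall alpha 0.05** (the documents give none).
- Mediation outside the Bonferroni family: 0.05.
- Two pairs: 0.05/2 = 0.025. Four pairs: 0.05/4 = 0.0125.
- All pairs: 0.05/22 = 0.0023 or 0.05/24 = 0.0021.
- Pairs and main effects in one family: 0.05/33 = 0.0015 or 0.05/36 = 0.0014.

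The two-pair count takes the closing words on continued smoking as naming an outcome. Those words may only describe the mediators, and continued smoking is not among the listed outcomes.

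**3. False positives if all pairs are tested at 0.05 with no other condition.** Under independence, 1 - 0.95^22 = 0.68 and 1 - 0.95^24 = 0.71. These are only upper guides, because the tests are correlated. A simulation used the planned 130 participants. Its assumed inputs were 65 per arm, no dropout, a baseline coefficient of 0.6 with error SD 0.8, mediators correlated 0.3, outcomes correlated 0.3, B = 0, and a percentile bootstrap. The chance of at least one false indirect effect over 22 pairs was:

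| Effect on the mediators | Chance |
|---|---|
| Neither moved | 0.03 |
| Both moved 0.3 SD | 0.37 |
| One moved 0.5 SD | 0.38 |
| Both moved 0.5 SD, outcome correlation 0.5 | 0.53 |
| Both moved 0.5 SD | 0.60 |

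A separate simulation gave 0.585 for the last row and 0.033 for the first, within Monte Carlo error.

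**4. The same risk with the promised correction applied.** At 0.05/22 with 5,000 resamples, the 0.60 becomes 0.043. At 0.05/4 the rate per test is 0.0099, so four pairs give at most 4 x 0.0099 = 0.04.

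**5. Power for one true pair** (A = 0.5 SD, B = 0.3), simulated:

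| Level | Power |
|---|---|
| 0.05 | 0.863 |
| 0.05/2 | 0.780 |
| 0.05/4 | 0.657 |
| 0.05/22 | 0.440 |
| 0.05/24 | 0.429 |

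A hand check treats the product as significant when both paths are:
- SE of A = 2 x 0.8/√130 = 0.140, so A/SE = 3.56.
- SE of B = 0.8/(0.8 x √130) = 0.088, so B/SE = 3.42.
- At 0.05 (critical value 1.96): Φ(1.60) x Φ(1.46) = 0.946 x 0.928 = 0.88.
- At 0.05/22 (critical value 3.052): Φ(0.51) x Φ(0.37) = 0.695 x 0.644 = 0.45.

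Both agree with the simulation. The verdict on such a pair depends on the level in 0.863 - 0.440 = 0.42 of simulated trials.

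**6. If mediation is examined only where there is an intervention effect to explain.** The plan speaks of mediators of intervention effects and defines path C, though it states no such condition. An approximate check replaced the bootstrap by joint significance of both paths (500 runs, both mediators moved 0.5 SD). The chance of any false indirect effect was 0.56 without the condition. It was 0.06 when path C also had to be significant at 0.05, and 0.01 when path C was required at 0.05/11.

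**The case for a change.** The strongest case for a change is that mediation is declared primary, the rule has no number, and a sentence or two would settle it without new data or participants. The plan itself hypothesizes that expectancies and norms will shift, so the setting where the product test runs at nominal size is the one the intervention is built to create. A level chosen late could also decide the verdict on a real mediator in about 42% of simulated trials.

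Much of this stands. The level is not stated, the pairs are not listed in the supplied text, and the simulation figures are right for their inputs. Three points reduce its weight.

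- The Bonferroni sentence speaks of alpha inflation generally. Confining it to main effects is an inference from the sentence before it.
- The plan calls the mediation effects hypothesized. The supplied text begins at recruitment and has no hypotheses section, so the absence of a list here does not show that none was fixed.
- The 0.60 needs both mediators moved by 0.5 SD and all 22 pairs tested with neither correction nor path C condition. The described feedback content covers norms but names no feedback on positive expectancies. Controls also receive the same smoking information without personalization, which may narrow the contrast on norms.

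The power loss under a large divisor is what any Bonferroni correction costs. It does not show that the plan chose wrongly.

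**Conclusion.** No change to the plan is called for. The scope and divisor of a promised correction are left unstated; no stated rule has been shown to be wrong. An analyst who applies that correction to the hypothesized pairs, whether 4 or all 22, keeps the chance of any false indirect effect at about 0.04 under the assumed inputs. One who reports mediation as explanatory, with intervals and no significance claims, is also on sound ground. The bad outcome (about 0.37 to 0.60 when the mediators are moved) requires testing every pair uncorrected, which disregards the plan's stated intention to control alpha inflation.

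The choices that remain are a short list against a full one (power 0.66 with 4 pairs, 0.44 with 22), confirmatory against explanatory status, and the type of bootstrap interval. Reasonable statisticians differ on each. All these figures rest on an assumed overall alpha of 0.05 and on assumed effect sizes, correlations and full retention, none of which the documents give. The conclusion also takes the mention of hypothesized effects to mean that the pairs are set out in text not supplied here.
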